5.6 Study visits

Table 4: Study visits

Visit time	Activity					
1st: Day 0	- Baseline assessments and recording					
	- Screening for presence pf plasmodium parasites (mRDT, qPCR)					
	- Parasite load assessment (rtPCR)					
	- Recruitment, randomization, and allocation.					
	 Treatment prescription and education on treatment administration. 					
2 nd : Day 7	- Parasite load measurement (rtPCR)					
	- Monitoring and recording of:					
	o ASEs and AEs.					
	 Treatment compliance /acceptability (dosage respect) 					
	 Number of withdrawals and reasons, 					
	 Occurrence of clinical symptoms 					
	 Concomitant medications 					
3 rd : Day 14	- Parasite load measurement (rtPCR)					
	- Monitoring and recording of:					
	 ASEs and AEs. 					
	 Treatment compliance /acceptability (dosage respect) 					
	 Number of withdrawals and reasons, 					
	 Occurrence of clinical symptoms 					
	o Concomitant medications					

4th: Day 28	- Parasite load measurement (rtPCR)			
	 Monitoring and recording of: 			
	- Wolltoring and recording or.			
	o ASEs and AEs.			
	 Treatment compliance /acceptability (dosage respect) 			
	 Number of withdrawals and reasons, 			
	Occurrence of clinical symptoms			
	 Concomitant medications 			
5 th : Day 35	- Parasite load measurement (rtPCR)			
	- Monitoring and recording of:			
	o ASEs and AEs.			
	 Treatment compliance /acceptability (dosage respect) 			
	 Number of withdrawals and reasons, 			
	 Occurrence of clinical symptoms 			
	 Concomitant medications 			

5.7 Laboratory tests

Before randomization during the baseline visit (D0), blood samples will be collected from each participant and examined for the presence of parasites (Gametocytes) using Malaria rapid diagnostic test kit (BIOCREDIT Malaria Ag P.f/Pan RDT). RDT positive samples will be re-examined with qPCR (quantitative polymerase chain reaction) and direct microscopy for confirmation. The qCPR will be repeated for negative samples and participants excluded if still negative. All qPCR positive samples will be further analyzed with rt PCR (real time polymerase chain reaction), for parasite quantification and specific stage identification, targeting specific parts of the gametocyte genes.

- a. *BIOCREDIT Malaria Ag P.f/Pan RDT*: This is a three-band RDT that detects HRP2 and pan-pLDH antigens which will detect the presence of P. falciparum (HRP2) and of another specie (pan-pLDH). Results will be interpreted as Negative (band absent) Mildly positive (faint band appearance) strongly positive (conspicuous band appearance).
- b. *Direct microscopy*: Direct Microscopic identification of parasites will be performed using thin and thick blood films stained with Giemsa and quantified as number of parasites per milliliter of blood.
- c. *rtPCR*): The parasite load will be measured based on the number of rtPCR cycle thresholds (Ct) (which is an inverse proportion of the parasite load) and classified as absolute increase in Cycle threshold (Ct >20), or negative rt-PCR tests results (Ct >40).
- d. *Blood sample schedule*: Five blood samples (approximately 1mL each) will be collected at Visit 1 (Day 0), Visit 2 (Day 7), Visit 3 (Day 14), Visit 4 (day 28), and visit 5 (day 35). After conducting the 3 or 4 tests at visit 1, only the rtPCR test and blood smear microscopy will be done during subsequent evaluations.

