2.3.2 Secondary objectives

- 1. To assess participants response (treatment efficacy) to varying dose concentrations, dose frequency, length of treatment, and formulation of *Artemisia afra* treatment.
- 2. To identify the most acceptable dose concentration, dose frequency, length of treatment, and formulation (flavor) of Artemisia treatment.
- 3. To assess the safety (ASE) of *Artemisia afra* treatment in participants by dose concentration, dose frequency, length of treatment, and formulation. As a commonly used tea, no toxicity is expected.
- 4. To assess variability of plasmodium test predictive values between mRDT, rtPCR, and direct blood smear observation in asymptomatic persons.

Treatment outcomes

Major outcome

• Decrease in parasite load over time.

Secondary outcomes

- Decrease in gametocyte load in carriers with Artemisia afra tea by dose concentration, dose frequency, length of treatment, and formulation.
- Acceptability (adherence and completion) of *Artemisia afra* treatment by dose concentration, dose frequency, length of treatment, and formulation (flavor).

- Safety (SAEs) of *Artemisia afra* treatment in participants by dose concentration, dose frequency length of treatment, and treatment formulation.
- Absolute increase in Cycle threshold (Ct >20).
- Likelihood and variability in the rate of reservoir elimination with treatment, compliance/ acceptability, and occurrence of side effects /adverse events in different treatment arms.

Treatment endpoints

Primary endpoints

• Proportion of people with decreased gametocyte load after treatment with *Artemisia afra* tea on Day 35 from baseline.

Secondary endpoints

- Level of decrease in gametocyte load (rt-PCR Ct) in the different treatment arms at D7, D14, D28, and D35 from baseline (activity level and optimal dosage schedule).
- Level of decrease in gametocyte load the various treatment arms (rt-PCR Ct) by gender, age, and trial entry parasite load, at D7, D14, D28, and D35 from baseline.
- Absolute increase in Cycle threshold (Ct >20) in various treatment arms at D7, D14, D28, and D35 from baseline.
- Proportion of people in the various treatment arms who respect and complete the prescribed treatment dosages (accepted dosage schedule and drug formulation).
- Proportion of persons on the various arms of treatment who develop clinical symptoms at D7, D14,
 D28, and D35 from baseline.

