- Proportion of people on the various arms of treatment who develop ASEs or AEs at D7, D14, D28, and D35 from baseline (No severe adverse side effects are expected).
- Proportion of persons on the various arms of treatment who withdraw from study due to severe ASEs or AEs at D7, D14, D28, and D35 from baseline.
- Proportion of persons on the various arms of treatment who withdraw from study for reasons other than severe AEs at D7, D14, D28, and D35 from baseline.
- Proportion of persons with baseline discordant test results (False positive or false negative) between mRDT, rt PCR, and direct blood smear observation?

Exploratory endpoints

- Variability in level of decease in gametocyte load (rt-PCR Ct) in the various treatment arms at D7, D14, D28, and D35 from baseline.
- Variability in level of decease in gametocyte load (rt-PCR Ct) in the various treatment arms by gender, age, and trial entry parasite load, at D7, D14, D28, and D35 from baseline.
- Variability in attainment of absolute increase in Cycle threshold (Ct >20) in the various treatment arms at D7, D14, D28, and D35 from baseline.

- Variability in the proportion of participant who respect and complete prescribed treatment dosages (acceptability) in the various treatment arms.
- Variability in the proportion of participants who develop clinical symptoms in the various treatment arms at D7, D14, D28, and D35 from baseline.
- Variability in the proportion of participants who develop Severe ASEs in the various treatment arms at D7, D14, D28, and D35 from baseline (not expected).
- Variability in proportion of participants who withdraw from the study due to severe ASEs, in the various treatment arms, at D7, D14, D28, and D35 from baseline.
- Variability in proportion of participants who withdraw from the study for reasons other than severe AEs, in the various arms of treatment at D7, D14, D28, and D35 from baseline.

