4. STUDY POPULATION

The study will be conducted at the University of Buea in Cameroon, and the University of Rwanda. All students and staff members of the University will be invited to participate. In the University of Buea, there are about 12,000 students and 973 staff members (500 teachers and 473 administrative /supporting staff. The University of Rwanda (UR) has about 30,445 students and 2,266 staff members (1450 teachers and 816 administrative /supporting). All students and staff members of the University will be invited to participate in the study. Participants will be included in the study if in good health as judged by physical examination and medical history, and if they meet all specified eligibility criteria.

Table 3: Inclusion and exclusion criteria.

Inc	Inclusion criteria for trial allocation groups		Exclusion criteria for trial allocation groups	
1.	Be student or worker of a participating	1. To have a known hypersensitivity to any ingredients		
	University.		of the tea.	
2.	Be 18 years and above, and in good general	2.	Currently taking a malaria drug for prevention or	
	health condition.		treatment.	
3.	Have a device (phone, tablet, etc) that will	3.	To have participated in another malaria drug trial or	
	support remote visits.		device in the last 14days.	
4.	Sign written informed consent form.	4.	To have a history or presence of clinically significant	
5.	Screened positive for malaria (RDT + and		medical, psychiatric, or emotional condition.	
	qPCR +) but asymptomatic.	5.	Reported diabetic.	

5-STUDY PROCEDURES

5.1 General considerations: The study will be conducted in accordance with the ethical principles for medical research involving humans in the World medical associations declaration of Helsinki (36). The study will be initiated only after approvals from relevant authorities, ethical and institutional review boards have been obtained. Freely given and written informed consent must be obtained from each participant prior to participation in the study.

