8. STATISTICAL CONSIDERATIONS AND ANALYSIS PLAN

8.1 Sample size calculations

As a pilot study, we will recruit 8 asymptomatic plasmodium carriers per study-arm in the 6 trial arms and 4 participants per arm in the 2 control (placebo) arms. Therefore 56 positive participants will be enrolled per site, making 112 participants in the whole study. To reach the required number of 56 gametocyte carriers, 635 persons will be RDT tested in Buea (south west region) where the expected positive RDT was 9.8% in Demographic health survey (DHS) 2018 (34) and drop-out rate was set at 10%. In Huye (South region) where the expected positive RDT was 6.9% in Malaria indicator survey (MIS) 2017 (35) and drop-out rate was set at 10%, 432 persons will be RDT tested to reach the required number of 56 gametocyte carriers.

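### Only RDT-positive samples go on to PCR and microscopy, so RDT false negatives and the predictive values of the three tests in the screened population are not estimable as promised; RDT positive predictive value and smear discordance among RDT positives are.

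*Protocol*

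**What the plan says.** Secondary objective 4 (Protocol section 2.3.2, with a counterpart in the Table 2 synopsis) is: "To assess variability of plasmodium test predictive values between mRDT, rtPCR, and direct blood smear observation in asymptomatic persons". The matching secondary endpoint, also in both places, is: "Proportion of persons with baseline discordant test results (False positive or false negative) between mRDT, rt PCR, and direct blood smear observation".

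Section 5.7 describes the Day 0 testing, and the study description in section 3 gives the same sequence:

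- Everyone has an RDT.
- The next step is reserved for one group: "RDT positive samples will be re-examined with qPCR (quantitative polymerase chain reaction) and direct microscopy for confirmation".
- Anyone in that group whose first PCR result is negative gets a second run: "The qCPR will be repeated for negative samples and participants excluded if still negative".
- The assay used to quantify parasites and identify their stage comes last and is narrower still: "All qPCR positive samples will be further analyzed with rt PCR".

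Eligibility (Table 3) needs both tests positive: the criterion begins "Screened positive for malaria (RDT + and" and goes on to require a positive qPCR. The visit schedule (Table 4) lists, for Day 0, "Screening for presence pf plasmodium parasites (mRDT, qPCR" without saying who gets which test.

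**The concern.** An RDT false negative is an infected person whose RDT is negative, and it takes a second test on that person to see one. In the written flow the second test depends on the first being positive. The objective and the sampling scheme therefore contradict each other. No later analysis plan can repair this, because the results would not exist.

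At stake is what the trial can say about RDT performance in asymptomatic carriers. The introduction calls accurate identification of this reservoir a critical step. If someone tabulated only the samples that have a reference result, the RDT false-negative cell would be empty whatever the truth, and a reader could take that as evidence that RDT screening misses nobody.

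**Working it through.** **1. Who is verified.** Following the sequence in sections 3 and 5.7:

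| Day 0 status | RDT | qPCR | Smear | rt-PCR |
|---|---|---|---|---|
| RDT− | yes | no | no | no |
| RDT+/qPCR− (after repeat) | yes | yes | yes | no |
| RDT+/qPCR+ | yes | yes | yes | yes |

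**2. Reproducing the screening numbers.** Section 8.1 states: "Therefore 56 positive participants will be enrolled per site". With drop-out d = 10% and RDT positivity p, the number to screen is 56 / (1 − d) / p.

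- Buea, p = 9.8%: 56 / 0.9 / 0.098 = 634.9, against the stated 635.
- Rwanda, p = 14.4% (synopsis and section 3): 56 / 0.9 / 0.144 = 432.1, against the stated 432.
- Rwanda, p = 6.9% (section 8.1): 56 / 0.9 / 0.069 = 901.8, which does not give 432.

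The 432 fits only 14.4%. That conflict is a separate matter, so both values are carried below.

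**3. Size of the unverified group.** RDT negatives = N × (1 − p).

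| | RDT+ | RDT− |
|---|---|---|
| Buea, 635 at 9.8% | 62.2 | 572.8 |
| Rwanda, 432 at 14.4% | 62.2 | 369.8 |
| **Total of 1,067** | **124** | **943 (88%)** |
| Rwanda, 432 at 6.9% | 29.8 | 402.2 |
| **Total of 1,067** | **92** | **975 (91%)** |

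**4. What this does to each quantity.** Everyone with a reference result is RDT-positive. Among them the RDT false-negative and true-negative counts are both empty, so apparent sensitivity is 100% and apparent specificity 0% regardless of the facts.

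As an illustration only, suppose a share f of RDT negatives is PCR-positive (assumed; the protocol gives no figure). Using the 943, f = 2% would mean 0.02 × 943 = 19 unseen false negatives, and f = 20% would mean 189. With an assumed positive predictive value of 0.7 to 0.9, true sensitivity would be 0.82 to 0.86 in the first case and 0.32 to 0.37 in the second. The RDT-by-qPCR table that the trial collects would look the same in both.

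**5. What survives.** RDT positive predictive value against qPCR has a 95% half-width of 1.96 × √(q(1 − q)/m). The values q = 0.7 and 0.9 are assumed.

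| RDT positives m | q = 0.7 | q = 0.9 |
|---|---|---|
| 62 (one site) | 11.4 points | 7.5 points |
| 124 (pooled) | 8.1 points | 5.3 points |
| 92 (pooled, Rwanda at 6.9%) | 9.4 points | 6.1 points |

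Smear against qPCR is also observed for every RDT positive, including smear-negative/qPCR-positive samples. Comparisons with rt-PCR exist only in RDT+/qPCR+ samples, so RDT false positives cannot be fully counted against rt-PCR, which is the PCR that the endpoint names.

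**The case against.** Four things speak for the protocol.

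*Some text could be read as testing RDT negatives.* The repeat of qPCR for negative samples might be stretched to cover them, Table 4 lists RDT and qPCR together, and section 5.7 mentions three or four tests at the first visit. None of this holds up. A repeat, and a result that is still negative, presuppose an earlier qPCR, so these are RDT+/qPCR− samples. Three or four tests fits the sequence: RDT, qPCR and smear, plus rt-PCR if qPCR is positive. Table 4 does not say that everyone gets both.

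*Figure 2, the screening flow, is not shown.* It could carry a branch for RDT negatives. That caveat stands, but no visible text supports such a branch.

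*The endpoint covers more than RDT false negatives.* This is right. A reader might infer that the whole objective is unanswerable, or that every mention of false negatives should be deleted. The documents do not support either: smear false negatives against qPCR among RDT positives are delivered by the design.

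*No misreport is written into the plan.* A reader might infer that the trial will report an RDT false-negative proportion of zero. The protocol defines no such table or denominator. The exact statement is that the quantity is not estimable; a zero arises only if verified samples are tabulated alone. Nor do the documents support a count of missed infections: that needs an RDT sensitivity from outside and, if all 124 RDT positives are taken as infected, a positive predictive value of 100%. The latter sits badly with a protocol that excludes RDT positives who stay qPCR-negative.

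Restricting the endpoint to enrolled participants does not help either. Eligibility requires RDT and qPCR both positive, so discordance between those two would then be absent by definition.

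**Conclusion.** The concern holds in a limited form. On the visible text, 88% to 91% of screened people have no reference result. RDT false negatives, negative predictive value, sensitivity and specificity cannot be estimated, and neither can any predictive value of smear or rt-PCR in the screened asymptomatic population. Part of objective 4 and of its endpoint is therefore undeliverable as worded.

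The conclusion depends on Figure 2 not adding a test for RDT negatives. It does not depend on which Rwanda positivity figure is right, nor on any assumed sensitivity.

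The weight is moderate. This is one secondary objective and one secondary endpoint in a pilot trial, and eligibility, randomisation, the primary endpoint, treatment comparisons and safety are untouched. It is still worth correcting before the trial starts, because the missing results cannot be recovered by analysis.

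**What to change.** Reword objective 4 and the discordance endpoint, in section 2 and in the Table 2 synopsis, as:

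- (a) RDT positive predictive value, that is false positives, against qPCR;
- (b) smear versus qPCR discordance among RDT positives, keeping smear false negatives;
- (c) smear versus rt-PCR discordance among RDT+/qPCR+ samples.

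Add one sentence stating that RDT false negatives, negative predictive value, sensitivity and specificity are not estimable under this screening flow. If Figure 2 does send RDT negatives to PCR, sections 3 and 5.7 should say so instead. The cost is the wording of one objective and one endpoint, each in two places.

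Only if the lost quantities are wanted: run qPCR and smear on a pre-stated random sample of RDT-negative Day 0 blood and weight by the sampling fraction. The blood is already drawn from everyone screened, so the cost is the extra qPCR and smear tests. This step is optional and is not needed to resolve the contradiction.

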This study will use the adapted Zelen design which has two steps in the consent process. At step one, informed individuals (students and workers) will be invited to participate in a screening and cohort survey on asymptomatic malaria, aimed at understanding the comportment of plasmodium parasite in asymptomatic plasmodium carriers over time. After informed consent is obtained during the first encounter (day 0), baseline assessments will be done and sociodemographic variables, clinical/medical history, physical assessment, prior medications information and participants' contact details will be recorded. Blood samples will be collected from each participant and examined for the presence of parasites (Gametocytes) using malaria rapid diagnostic test kit (mRDT). RDT positive samples will be re-examined with qPCR (quantitative polymerase chain reaction) and direct microscopy for confirmation. The qCPR will be repeated for negative samples and participants excluded if still negative. All qPCR positive samples will be further analyzed with rt PCR (real time polymerase chain reaction), for parasite quantification and specific stage identification, targeting specific parts of the gametocyte genes. Participants who fulfil the inclusion criteria will be randomly allocated in the 8 study arms in a 2:2:2: 2:2:2: 1:1 ratio for the 6 treatment and 2 control arms, respectively. In the second step, only participants from the intervention groups (TG1- to -TG7) will receive the information about the intervention and a second consent will be obtained from them. Treatment administration will be based on the allocation arm. The treatments will consist of Artemisia afra tea infusions for the 6 trial arms versus favored placebo infusions and desired regular tea for the 2 control arms. The participants who will decline to participate to an intervention will continue in the cohort study, as a control group on regular tea (TG 8).

Screening and recruitment: Screening will be done during at baseline visit (Day 0) in the health stations set up in the study sites. After informed consent is obtained, baseline assessments will be performed to obtain information on sociodemographic characteristics, clinical/medical history, physical assessment, prior medications, and participants' contact details. This will be followed by screening tests for presence of plasmodium parasites. Participants who fulfil the inclusion criteria will be enrolled in the study.

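### Among RDT-positive persons, the mRDT versus rt-PCR part of the baseline discordance endpoint cannot contain a true RDT false positive, and on its stated gametocyte target it counts confirmed infections without gametocytes as discordant

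*Protocol*

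**What the plan says.** The fourth secondary objective (Protocol 2.3.2) is: "To assess variability of plasmodium test predictive values between mRDT, rtPCR, and direct blood smear observation in asymptomatic persons". Its endpoint, listed among the secondary endpoints in section 2 and in the synopsis, is: "Proportion of persons with baseline discordant test results (False positive or false negative) between mRDT, rt PCR, and direct blood smear observation". qPCR is not one of the three tests, and no reference test or denominator is named.

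Section 5.7 fixes the order of testing at Day 0:

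- Each sample with a positive RDT goes to both qPCR and microscopy.
- The rule for a negative qPCR reads: "The qCPR will be repeated for negative samples and participants excluded if still negative".
- Only samples that pass this step receive rt-PCR, an assay described as "targeting specific parts of the gametocyte genes".

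Section 5.7(a) describes the RDT as an HRP2 and pan-pLDH antigen test. Section 5.7(c) calls rt-PCR negative at Ct above 40. Table 3 (section 4) makes a positive RDT and a positive qPCR the entry condition; gametocyte carriage is not required.

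The rt-PCR is described in two ways. Sections 3 and 5.7 give it a gametocyte target, and the secondary endpoints equate gametocyte load with rt-PCR Ct. Yet section 5.7(c) says "The parasite load will be measured based on the number of rtPCR cycle thresholds (Ct", and Table 4 also calls it a parasite load measurement.

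**The concern.** A discordance endpoint that speaks of false positives should be able to find a positive RDT in a person without parasites, and should not count a correct positive RDT as an error. The mRDT/rt-PCR comparison does neither. Persons who could be true RDT false positives leave the pathway before rt-PCR. Those who remain are all qPCR-positive, and some will be rt-PCR-negative only because that assay looks for a different parasite stage.

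Calling such a pair an rt-PCR false negative instead would not help: the rt-PCR would be right that there are no gametocytes. Either label presents a difference in target as a test error. At stake is the RDT error rate reported under objective 4.

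**Working it through.** **1. The plan's own figures.** Number to screen = 56 / RDT positivity / (1 − 0.10).

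- Buea: 56 / 0.098 / 0.90 = 634.9; the protocol states 635.
- Rwanda at 14.4% (synopsis, section 3): 56 / 0.144 / 0.90 = 432.1; the protocol states 432.
- Rwanda at 6.9% (section 8.1): 56 / 0.069 / 0.90 = 901.8, which does not match the 432 given there.

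These calculations treat every RDT-positive as a gametocyte carrier, so they supply no estimate of the share without parasites or without gametocytes.

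Expected RDT-positives: 635 × 0.098 = 62.2 in Buea; 432 × 0.144 = 62.2 or 432 × 0.069 = 29.8 in Rwanda. The total is about 92 to 124.

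**2. Following each kind of RDT-positive person through section 5.7.** A positive qPCR is taken as infection, as Table 3 does, and rt-PCR is taken to read gametocyte genes only.

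| RDT-positive person | qPCR | rt-PCR | mRDT/rt-PCR pair | mRDT/smear pair |
|---|---|---|---|---|
| (a) No parasites | negative twice, excluded | not run | none | discordant |
| (b) Infected, no gametocytes | positive | negative (Ct above 40) | discordant | concordant, or discordant if the smear misses it |
| (c) Infected, gametocytes present | positive | positive | concordant | concordant, or discordant if the smear misses it |

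Group (a), the only true RDT false positives, contributes nothing to the mRDT/rt-PCR pair. All discordance in that pair comes from group (b). This follows from the testing order and does not depend on any prevalence. In the mRDT/smear pair, group (a) does appear, mixed with infections the smear missed.

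**3. Size for 62 RDT-positives (one site).** The following are assumptions, not protocol figures: share without parasites f = 5–30%; share of the infected without gametocytes g = 20–70%; smear sensitivity among the infected s = 30–80%.

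- True RDT false positives, 62f: 62 × 0.05 = 3.1 to 62 × 0.30 = 18.6. None has an rt-PCR result.
- Infections without gametocytes, 62(1 − f)g: 62 × 0.70 × 0.20 = 8.7 to 62 × 0.95 × 0.70 = 41.2.
- Apparent RDT false-positive share in the mRDT/rt-PCR pair: g, that is 20–70%, against a true f of 5–30%.
- mRDT-positive/smear-negative, 62f + 62(1 − f)(1 − s): 3.1 + 58.9 × 0.20 = 14.9 to 18.6 + 43.4 × 0.70 = 49.0. True false positives make up between 3.1 / 44.3 = 7% (f = 5%, s = 30%) and 18.6 / 27.3 = 68% (f = 30%, s = 80%).

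For both sites together, the same assumptions give 92 × 0.05 = 4.6 to 124 × 0.30 = 37.2 true false positives, and 92 × 0.70 × 0.20 = 12.9 to 124 × 0.95 × 0.70 = 82.5 infections without gametocytes.

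**The case against.** **The endpoint has a third test.** A reader might infer that the endpoint as a whole cannot show a true RDT false positive. The documents do not support that. Every RDT-positive sample goes to microscopy, the Enrolled Population (8.2.1) keeps screened persons whatever their randomization status, and section 9.4 requires an eCRF for each screened person who consents. A parasite-free RDT-positive can therefore appear as mRDT-positive/smear-negative. This stands, and it limits the point to the mRDT/rt-PCR comparison. It does not rescue that comparison, and the smear alone cannot say which discordant persons are uninfected.

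**The one-sided qPCR repeat.** A reader might also infer that rerunning only negative qPCRs causes the distortion. It does not, since qPCR is not a compared test. The repeat would help if qPCR became the comparator. Suppose everyone is infected (true RDT false positives 0%) and runs are independent. At an assumed single-run sensitivity of 90%, the first run alone shows 10% discordance and the result after repeat 0.10² = 1%. At 80% the figures are 20% and 0.20² = 4%. The repeat moves the answer towards the truth.

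**rt-PCR may detect all stages.** Some passages call it a parasite-load measure. If that is what it measures, the mislabelling of non-carriers falls away, but the absence of true false positives from the pair remains. Section 3 links the two descriptions by using gametocyte-gene tests to set the baseline parasite load, so the gametocyte reading has more support. The conflict needs settling either way.

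**Reference test and denominator can be left to a SAP.** That is fair, and their absence alone is not the point. But the gate before rt-PCR is a laboratory step fixed in the protocol, and no analysis plan can supply results that were never generated.

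**Conclusion.** The concern holds for the mRDT versus rt-PCR comparison among RDT-positive persons. That comparison contains no true RDT false positive, provided a positive qPCR means infection. If rt-PCR reads gametocyte genes only, as the protocol mostly says, and an rt-PCR-negative result is taken to make the RDT false, it also counts correct RDT results as errors. The mRDT/smear comparison does contain the true false positives but cannot isolate them.

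The affected group is about 92 to 124 RDT-positives. The split within it is unknown, so the counts above are illustrations under stated assumptions. Only one descriptive secondary endpoint is touched, not the primary endpoint, but it would give a misleading answer to a stated objective, and it can be corrected with data already planned.

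**What to change.** For RDT-positive persons, reword the endpoint as follows:

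1. Compare mRDT and smear with the final qPCR result, that is after the repeat, and show the first-run result alongside.
2. Keep persons excluded as qPCR-negative in the denominator.
3. Report rt-PCR separately, as gametocyte carriage among the qPCR-positive.
4. Reconcile the passages that call rt-PCR a parasite-load measure with those that call it a gametocyte measure.

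First-run qPCR should not be the sole comparator, because infections it missed would then be counted as RDT errors. The cost is a change of wording, and the reported discordance may differ from what the present endpoint would give. No extra test is needed: qPCR and microscopy are already planned for every RDT-positive sample.
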